9.2.4 Participant Follow-up

For the vaccinated and concurrent control arms, study participants will be followed from the index date to the end of the study, loss to follow-up (deregistration), vaccination (for unvaccinated controls), vaccination of the matched control (for vaccinated people), or death, whichever is earlier.

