9.7.6.2 Health Care Resource Use and Health Care Cost Related to COVID-19

The objective of the economic analysis will be to estimate incremental health service use and incremental health service costs associated with receipt of at least one dose of the Oxford/AstraZeneca COVID-19 vaccine (the AstraZeneca vaccine arm) or at least one dose of other COVID-19 vaccines (the other COVID-19 vaccine arm) over the short (one and three months of follow-up) and medium term (six months of follow-up) and to disaggregate incremental costs by cost category. Our comparator groups and their construction will mirror those proposed for the statistical analyses, namely: (i) the AstraZeneca vaccine arm; (ii) the other COVID-19 vaccine arm; (iii) the concurrent control arm. The approaches to matching participants based on age group, gender, region, comorbidity status and practice, and to defining the date of study entry, will mirror those proposed for the statistical analyses.

Cumulative health care service use and health care costs covering primary and secondary health care services over 1 month, 3 months and 6 months of follow-up will be estimated using data extracted from the data assets listed in Section 9.4, and grouped by the following clinical settings and resource categories:

- Primary care consultations;
- Primary care prescriptions;
- Primary care medical tests and investigations;
- Hospital outpatient attendances and procedures;
- Hospital A&E (emergency department) attendances without admission
- Hospital admissions, inpatient, and day cases.

Primary and secondary care services will be valued by attaching unit costs derived from national compendia to resource inputs. All costs will be expressed in pounds sterling and valued at 2021 prices with unit costs estimated at earlier price dates inflated to 2021 prices using the NHS Hospital and Community Pay and Prices Index.

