Characteristics of each comparator group will be compared using t-tests for continuous variables and chi-square tests for categorical variables. Initial exploration of the data will be conducted to guide selection of the appropriate analytic strategy. Inverse probability weighted GEE (Salazar et al., 2016) will be used to model non-linear trends in healthcare service use and costs over time, accounting for missing data, and adjusting for the matching variables and BMI status, smoking status, and frailty score. In the models, the total follow-up period will be divided into time intervals and interval-specific weights calculated as the inverse cumulative product of the probability of being observed up to a given interval using the method of van der Wal and Geskus (2011). Inverse probability weighting ensures that observations with a high probability of being missing (for example costs incurred in the later months of follow-up) are given more weight than observations with a low probability of being missing (for example costs incurred in the earlier months of follow-up) (Glick et al., 2015).

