Adjusted estimates of cumulative healthcare utilisation counts, lengths of stay and costs, and between-group difference in counts, length of stay and costs, will be obtained from the regressions by summing interval-specific estimates over the time period of interest, a strategy originally reported by Lin (2000). Standard errors and confidence intervals around the mean estimates will be obtained via the robust variance/sandwich estimator, which provides a degree of robustness to departures from normality of errors and misspecification of the GEE working correlation matrix. An alternative approach for estimating standard errors and 95% confidence intervals is through the use of non-parametric bootstrapping. This would involve randomly sampling individual patients with replacement from the data to generate, for example, 1000 replicate datasets, and then fitting regression models to each replicate dataset and calculating adjusted bootstrap estimates of cumulative counts, lengths of stay and costs and the respective between-group differences. However, we recognise that the non-parametric bootstrap method can be computationally expensive for large sample applications such as ours. As a sensitivity check of the results generated by our primary modelling approach, we will therefore also apply the nonparametric bootstrap method to a smaller sample of data to obtain bias-corrected standard errors and confidence intervals. For completeness, the analyses will be repeated by restricting to patients with complete data over 1, 3 and 6 months of follow-up. The approaches to handling potential confounding will mirror those adopted by the statistical analyses. The analyses will also be repeated by the subgroups pre-specified by the statistical analyses.

We will also report the health care resource use and health care costs by COVID-19 risk group, using the JCVI risk group classification.

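### Section 9.7.6.2 guards against a misspecified GEE working correlation only through the sandwich estimator, which with interval-specific weights protects the standard errors but not the cost estimates

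*Protocol*

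**What the plan says.** Protocol section 9.7.6.2 specifies inverse-probability-weighted GEE, which "will be used to model non-linear trends in healthcare service use and costs over time, accounting for missing data". The model uses "interval-specific weights calculated as the inverse cumulative product of the probability of being observed up to a given interval", and the section explains that "observations with a high probability of being missing (for example costs incurred in the later months of follow-up) are given more weight". A person's weight therefore differs between intervals.

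Cumulative counts, lengths of stay and costs for each group, and the differences between groups, are "obtained from the regressions by summing interval-specific estimates over the time period of interest". The horizons are 1, 3 and 6 months.

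On inference the section says: "Standard errors and confidence intervals around the mean estimates will be obtained via the robust variance/sandwich estimator". It adds that this estimator "provides a degree of robustness to departures from normality of errors and misspecification of the GEE working correlation matrix". No working correlation structure is named. Two checks are planned: a bootstrap of standard errors and intervals in a smaller sample, and a rerun in patients with complete data.

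Comparator groups and matching follow the main analysis. Under section 9.2.4, follow-up ends at the end of the study, deregistration or death, and also at "vaccination (for unvaccinated controls), vaccination of the matched control (for vaccinated people").

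**The concern.** In an unweighted GEE with complete data, a wrong working correlation costs efficiency but leaves the mean estimates consistent, so a sandwich variance is all that is needed. Weights that vary within a person, combined with dropout, change this. The working correlation then decides how residuals from different intervals are combined after weighting, and that can move the point estimate even when the weights are exactly right. A sandwich variance would give an interval centred on the wrong value.

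The outputs at stake are the arm-level cumulative use and cost and the incremental use and cost. An analyst who relies on section 9.7.6.2 could choose an exchangeable or AR(1) structure and believe the risk was covered. Neither planned check would show otherwise. The bootstrap refits the same weighted model and addresses its standard errors and intervals. The complete-data rerun selects on follow-up and does not vary the working correlation, so a discrepancy could not be traced to it.

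**Working it through.** The protocol states no figure on this point, so there is none to reproduce. It gives no retention, within-person correlation, cost variance or strength of dependence of dropout on cost. All numerical inputs below are assumptions.

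**Why the estimate can move.** Let r_t be the residual in interval t, O_t = 1 if the interval is observed, p_t the true cumulative probability of being observed given the past, and w_t = O_t/p_t.

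- Independence: each term is w_t r_t. Its expectation is E[r_t] = 0, so the estimate is consistent.
- Form (a), W^½ R_obs⁻¹ W^½: the cross-terms contain √(w_s w_t) r_s. For s < t the expectation is proportional to E[√(p_t/p_s) r_s] if the correlation coefficient is held fixed. When dropout after s depends on cost in s, p_t/p_s varies with r_s and this is not zero.
- Form (b), R_obs⁻¹ W: the coefficient on w_s r_s depends on how many later intervals are observed, which again depends on r_s.
- Form (c), R_full⁻¹ W, with unobserved residuals weighted zero: each row is a fixed combination of the terms w_t r_t, so the estimate is consistent under any correlation.
- If dropout depends only on covariates in the mean model, p_t is constant given those covariates and all forms are consistent.

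**Simulation 1: dropout driven by each person's own past cost.** 1,000,000 persons, 6 monthly intervals, skewed costs with SD 100, within-person correlation 0.5, true weights, dropout more likely after a costly month. True totals are 640 (control) and 510 (vaccinated), a difference of 510 - 640 = -130. Working correlations were exchangeable 0.2 and 0.5, and AR(1) 0.5.

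| Dropout mechanism | Independence, bias in difference | Forms (a), (b), bias in difference | Form (c), bias in difference |
|---|---|---|---|
| Depends on past cost equally in both arms | 1.2 | -1.8 to 0.8 | 1.2 |
| Half as strongly in vaccinated arm | -1.9 | -17.2 to -46.1 (13% to 35%) | -1.9 |
| Not at all in vaccinated arm | -1.6 | -31.6 to -73.6 (24% to 57%) | -1.6 |
| Depends on arm only | 0.2 | 0.2 to 0.5 | 0.2 |

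In the first row the difference is safe but the arm totals are not. Under forms (a) and (b) they are too high by between 29.3/640 = 5% and 69.2/510 = 14%.

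**Simulation 2: pairs censored at the control's vaccination.** Here the censoring event depends on the control's last-interval cost and not on the vaccinated partner's. Control vaccination is less likely after a costly month. True difference -60, true weights. Slopes are log-odds per SD of cost.

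| Assumed inputs | Working correlation | Estimate at slopes 0.1, 0.25, 0.5 |
|---|---|---|
| Correlation 0.5, about 11% of pairs left at 6 months, skewed costs | Independence | -60, -61, -59 |
| Same | Exchangeable 0.5, form (a) | -49, -35, -13 |
| Same | Exchangeable 0.5, form (b) | -52, -41, -21 |
| Correlation 0.5, about 36% left | Independence | about -60 at each |
| Same | Exchangeable 0.5 | about -51, -41, -21 |
| Correlation 0.1, about 75% left, normal costs, SD 100 | Exchangeable 0.1, forms (a) and (b) | between -56 and -60 |

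With 36% left, the bias as a share of the true difference is (60 - 51)/60 = 15%, (60 - 41)/60 = 32% and (60 - 21)/60 = 65%. With 75% left and low correlation it is at most (60 - 56)/60 = 7%. The largest value seen was an estimate of about -1, a bias of 59/60 = 98% (form (a), normal costs, correlation 0.5, about 12% left, slope 0.5). Simulation noise is about 2 units.

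The direction is not fixed either. Dropout that is more likely after a costly month pushed the difference away from zero in simulation 1, and the opposite dependence pulled it toward zero in simulation 2.

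**The case against.** The strongest reply is that nothing wrong has been chosen. The sentence about robustness has standard errors and confidence intervals as its subject, claims only a degree of protection, and is correct as it stands. No working correlation is named, so independence is not excluded. The structure is ordinary SAP content, and the section says the data will first be explored to guide the analytic strategy. Bias also needs several things together: a non-independence structure, form (a) or (b), dropout that depends on earlier cost and, for the difference, a mechanism that differs by arm. The section cites a guideline on weighted GEE with dropout, whose recommended form cannot be seen here. This is an extension objective and not the primary effectiveness analysis.

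Much of this stands. A reader might infer that the protocol calls a wrong working correlation harmless; it does not. A reader might also infer that any non-independence structure biases the result. Form (c) and covariate-only dropout show that it need not, and with equal dropout mechanisms the difference is almost unaffected.

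What remains is that the protocol itself fixes weights that vary within a person, itself raises misspecification of the working correlation, and answers it only with a tool that repairs the variance. Leaving the structure to the SAP would be no fault. Offering a safeguard that does not cover the point estimates is more than missing detail.

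**Conclusion.** The point holds in limited form. With interval-specific weights, the sandwich estimator protects the standard errors only, and section 9.7.6.2 offers nothing that protects the point estimates from the choice of working correlation. Where dropout depends on earlier use or cost, a non-independence structure applied through form (a) or (b) can bias the arm-level totals. It can bias the between-arm difference when the mechanism differs by arm. Section 9.2.4 makes that plausible, because the control's vaccination ends follow-up for both members of the pair. The documents do not show that control vaccination depends on recent cost.

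The size cannot be derived from the protocol. Under assumed inputs it ran from negligible to nearly the whole true difference, and the percentages also depend on the assumed ratio of the difference to the cost SD. A reader might take one of these percentages as the expected bias in this study; the documents do not support that. The point concerns the cost and resource-use extension and has no bearing on the vaccine effectiveness estimates. It should be corrected before the cost models are fitted.

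**What to change.** In section 9.7.6.2, state that the weighted GEE will use an independence working correlation, or a weighting form shown to give consistent estimates with interval-specific weights, together with cluster-robust standard errors. Reword the robustness sentence so that it applies explicitly to the standard errors and confidence intervals and makes no claim about the point estimates.

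This takes a sentence or two of protocol or SAP text and no new data. The price is a small loss of efficiency, minor at the sample size described in section 9.5.

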The adenovirus vector ChAdOx1 vaccine technology has been used in the past for the development of candidate vaccines against several infections, including influenza, Zika, and MERS (Antrobus et al, 2014, Folegatti et al, 2020, López-Camacho et al, 2018). Oxford University has adapted and transferred the platform technology used against MERS-CoV to develop a vaccine against SARS-CoV-2, resulting in the rapid development of a vaccine against this infection. The Oxford/AstraZeneca COVID-19 vaccine (AZD1222) is a recombinant replication-defective chimpanzee adenovirus expressing the SARS-CoV-2 S surface glycoprotein (Folegatti et al, 2020). AZD1222 has been shown to be highly efficacious in pivotal randomized clinical trials (RCT), demonstrating 82% overall efficacy against symptomatic infection and 100% efficacy against severe infection. Recent unpublished data from the phase 3 pivotal trial in the United States showed high efficacy (85%) in people 65 years of age or older, and again confirmed 100% efficacy in preventing severe cases. Although a high level of single dose efficacy has been demonstrated in clinical trials between 3 and 12 weeks and confirmed in early effectiveness studies conducted in the United Kingdom (UK), clinical trials and effectiveness study so far have not included detailed vaccine-specific analysis by age group, co-morbidities, nor have they assessed vaccine impact on critical care admission, mortality, and overall outcomes. Similarly, there are few studies taking into account the COVID-19 variant, these data have been aggregated on a national basis by the UK COVID-19 Genomics consortium (UK COG) since September 2020 (Mishra et al, 2021). Thus, it remains important to better understand VE by ages, time intervals between doses, and to determine if single dose effectiveness may extend beyond 12 weeks.

Given mortality due to COVID-19 is highest in long-term care and assisted living facilities and since the Oxford/AstraZeneca vaccine is prioritized for these facilities due to its ease of reach, it is useful to understand the impact of Oxford/AstraZeneca vaccination on hospitalization and mortality for elderly people in these facilities. It's also important to assess VE by age groups and comorbidities for best guidance for COVID-19 immunization programs.

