9.7.2 Stratification/Subgroup Analyses

Stratifications/subgroup analyses will be fully detailed in the SAP, and may include:

- Age: <12, 12-16, 16-49, 50-64, 65-69, 70-79, 80+; or 16-39, 40-<49, 50+, 65+, 80+
- Comorbidity
 - o categories of the CMMS
 - specific comorbidities known to indicate high risk for COVID-19 infections and/or suboptimal response to vaccine, in accordance with National guidance from UK Health Security Agency (UKHSA, 2021) or other, including chronic respiratory disease, chronic kidney disease, chronic heart disease and vascular disease, chronic liver disease, chronic neurological disease, diabetes mellitus, severe mental illness, morbid obesity, asplenia or dysfunction of the spleen, and immunosuppression due to disease or treatment.
- Immunosuppressant prescribed medication: current vs. past use, regimen
- Long-term care or assisted living care residents (if possible)

Stratifications/subgroups in the vaccinated population may include:

- Heterologous dosing
- Vaccine dose: people receiving 1 dose only, ≥1 dose, 2 doses, booster/other additional doses
- Intervals after the 1st dose among people receiving 1 dose only: 0-7, 8-14, 15-21, 22-28, 29-35, 36-42, 43-49, 50-70, 71-77, 78-84 days post dose 1, and/or other combinations may be used
- Interval between doses among people receiving 2 (or more) doses: 21 to 41, 42 to 69, 70 to 77, 78 to 84, over 84 days and/or other combinations may be used.
- Vaccine batch number
- Aged over 65 by electronic frailty index (eFI) categories (mild, moderately, and severely frail)

Stratification/subgroups in the population with COVID-19 may include:

- COVID-19 severity
- COVID-19 variant

Subgroup analyses will only be conducted if sufficient events for an outcome within the subgroup allows.

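### The subgroup rule for the use and cost contrasts has no exception for COVID-19 severity and variant, which arise after vaccination; vaccine contrasts within those strata would leave out the saving from averted and milder cases

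*Protocol*

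**What the plan says.** Protocol section 9.7.6.2 sets out to estimate "incremental health service use and incremental health service costs associated with receipt of at least one dose of the Oxford/AstraZeneca COVID-19 vaccine", or of another COVID-19 vaccine, over one, three and six months. The groups are the AstraZeneca arm, the other-vaccine arm and the concurrent control arm. Matching and study entry follow the effectiveness analysis, and hospital admissions are one of the cost categories. After describing the models, the section states: "The analyses will also be repeated by the subgroups pre-specified by the statistical analyses". It names no exception.

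The protocol's only list of subgroups is in section 9.7.2, which opens: "Stratifications/subgroup analyses will be fully detailed in the SAP, and may include". It has three parts: general subgroups, subgroups of the vaccinated population, and a third part introduced by "Stratification/subgroups in the population with COVID-19 may include", whose entries are COVID-19 severity and COVID-19 variant. One condition applies to the whole list: "Subgroup analyses will only be conducted if sufficient events for an outcome within the subgroup allows".

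Section 7 reports earlier trials of the AstraZeneca vaccine as "demonstrating 82% overall efficacy against symptomatic infection and 100% efficacy against severe infection". Section 9.3.2 makes COVID-19 hospitalization, ICU admission and death the primary effectiveness outcomes.

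**The concern.** The economic question is what follows, in use and cost, from being vaccinated. The clock starts at the index date, which for the vaccinated is the first dose. Whether a person then becomes a COVID-19 case, and how severe the case is, are results of exposure that vaccination is expected to change. They lie on the path from vaccination to cost, and severity overlaps the cost outcome itself through hospital admissions.

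A comparison of arms among people who all had severe disease, or all had mild disease, holds that path fixed. Infections that did not happen, and cases that were mild instead of severe, cannot appear in it. The people compared also differ: a vaccinated severe case is someone in whom the vaccine did not prevent severe disease, while an unvaccinated severe case is drawn from everyone exposed. A table of incremental cost by severity could show little saving, or even an excess, and be read as evidence that vaccination does not reduce resource use.

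**Working it through.** **Textual check**

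1. Section 9.7.6.2 repeats the arm contrasts by the statistical subgroups, worded as something that will be done.
2. Section 9.7.2 is the only place in the protocol where those subgroups are listed. Severity and variant are there, as possibilities, for people with COVID-19.
3. The sole filter in section 9.7.2 is enough events. Nothing separates subgroups fixed before vaccination from those that arise after it.
4. Section 9.2.3 excludes people infected before vaccination from the primary analysis. In a cohort built that way, a vaccinated person enters the COVID-19 population only after the index date. Restricting to cases is therefore already conditioning on a post-vaccination event, before any split by severity.

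An SAP that adopted the section 9.7.2 list and followed the section 9.7.6.2 rule would produce a vaccine-versus-control cost contrast by severity.

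**Size**

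The protocol states no cost or event figure here, so there is nothing to reproduce. Every input below is assumed, for illustration:

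- six-month infection risk without vaccine, r = 5%
- share of infections that are severe without vaccine, s = 6%
- cost per mild case GBP 100, per severe case GBP 6,000
- effectiveness against infection, 30% to 60%
- effectiveness against severity given infection, 50% to 80%

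Cost per case = (1 − s) × 100 + s × 6,000. COVID-19 cost per person = r × cost per case. Background cost is taken as equal in the arms and cancels.

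Unvaccinated: per case 0.94 × 100 + 0.06 × 6,000 = 454; per person 0.05 × 454 = 22.7.

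Vaccinated, lower effectiveness (30%, 50%): r = 0.035, s = 0.03; per case 97 + 180 = 277; per person 0.035 × 277 = 9.7. Saving: 22.7 − 9.7 = 13.0 per person, and 454 − 277 = 177 per case.

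Vaccinated, higher effectiveness (60%, 80%): r = 0.02, s = 0.012; per case 98.8 + 72 = 170.8; per person 0.02 × 170.8 = 3.4. Saving: 22.7 − 3.4 = 19.3 per person, and 454 − 170.8 = 283.2 per case.

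| Contrast (GBP) | Equal cost at a given severity | Vaccinated cases cost 10% less at each severity |
|---|---|---|
| Whole cohort, saving per person | 13.0 to 19.3 | 14.0 to 19.6 |
| All cases, saving per case | 177 to 283 | 205 to 300 |
| Mild stratum, saving per case | 0 | 10 |
| Severe stratum, saving per case | 0 | 600 |

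The zero follows from assuming equal case costs, so it shows the mechanism and is not an estimate. The last column shows what survives stratification: only the cost difference between cases of equal severity. The all-cases row has already lost the averted infections: it depends only on effectiveness against severity, whether effectiveness against infection is 30% or 60%. The illustration leaves out selection, whose size the protocol gives no means to gauge.

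**The case against.** The strongest reply is that the protocol never states a vaccine contrast by severity. The list is provisional and left to the SAP. Its three parts are tied to different populations, and the vaccinated-population part, such as batch number, cannot be applied to unvaccinated controls, so the list was plainly not written for mechanical use on every contrast. Severity has proper uses elsewhere, for example the description of long COVID in section 9.7.6.4. A reader might infer that a by-severity contrast is already committed to; the text supports only that the rule would admit it. That much of the reply stands. It does not dispose of the point, because the fault is in the rule: section 9.7.6.2 takes over the statistical list without exception, and that list serves several purposes.

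Variant is a weaker case than severity. Section 9.7.5 describes effectiveness by combinations of region and period, which does not condition on a person's own infection. Only individually determined variant shares the problem.

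The models in section 9.7.6.2 adjust for frailty score, which would reduce selection among cases. But Table 6 makes the score available only from age 65, and adjusting for frailty does not restore averted cases.

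It is also tempting to confine the contrasts to subgroups known at the index date. Read literally, that would delete number of doses and interval between doses, which are strata of the primary and secondary objectives. The point made here does not require it.

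**Conclusion.** The point holds for the subgroup results and no further. The rule in section 9.7.6.2 admits vaccine contrasts within COVID-19 severity and individually determined variant. Such contrasts would omit the saving from averted infections and from milder disease, and would compare selected cases.

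Two stronger readings are not supported. One is that the economic analysis loses the saving it is meant to measure: the whole-arm incremental cost over one, three and six months stays as planned, as does the reporting by JCVI risk group. The other is that the whole saving always vanishes within strata: this is so only if a case of given severity costs the same in both arms.

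The conclusion rests on vaccination altering infection and severity, which the protocol's own background and choice of primary outcomes take as expected, and on the SAP keeping severity or variant on its list. The pound figures are assumed. The risk is a misleading secondary table, which one sentence in the protocol can prevent.

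**What to change.** Replace the subgroup sentence in section 9.7.6.2 with:

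> The vaccine contrasts in use and cost will be repeated by the pre-specified subgroups, except those defined in the population with COVID-19 (severity, individually determined variant). These will be used to describe use and cost per COVID-19 case from the infection date, and any comparison by vaccination status among cases will be labelled descriptive and not as the incremental effect of vaccination.

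Strata by dose number, dose interval, booster and heterologous dosing are not removed by this wording. A comparison of breakthrough with unvaccinated cases remains possible under its proper label.

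The cost is a wording change in the protocol, carried into the SAP, with no new data. What is given up is reporting by-severity incremental contrasts as effects of vaccination.
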